6.1.1.2 General Informed Consent

Consent must be documented by the subject's dated signature or by the subject's legally acceptable representative's dated signature on a consent form along with the dated signature of the person conducting the consent discussion.

A copy of the signed and dated consent form should be given to the subject before participation in the study.

The informed consent form and any written information provided to the subject must receive the IRB/ERC's approval/favorable opinion in advance of use. The subject or his/her legally acceptable representative should be informed in a timely manner if new information becomes available that may be relevant to the subject's willingness to continue participation in the study. The communication of this information will be provided and documented via a revised consent form or addendum to the original consent form that captures the subject's dated signature or by the subject's legally acceptable representative's dated signature.

Specifics about a study and the study population will be added to the consent form template.

Protocol/Amendment No.: 1.1 (14 Sep 2019)

VEAP ID NO: 8439

Epidemiology No.: EP05026.058

The informed consent will adhere to IRB/ERC requirements, applicable laws and regulations and Sponsor requirements.

The ICF for the study will be finalized upon receiving agreement on the final protocol from Taiwan CDE.

6.1.1.3 Baseline data collection

A CRF will be developed by a qualified vendor (TBD) and used to collect information at baseline, the time at enrollment. Each patient is assigned a unique identification number, which is exclusively used for study purpose. For the study duration and afterwards, only the investigators or authorized site study personnel will have access to the key linking the study unique identification number back to the patient's identity to identify the patient.

Demographic characteristics, vital signs, and ECOG physical performance score will be assessed and recorded by investigators or other study staff at the baseline visit. MSI/MMR test method and results, laboratory test results, the diagnosis, histology, staging, and treatment history of cancer, along with any disease-specific categorization information and comorbidity will be extracted from the medical records/EHR if available. The investigators will attempt to collect the information that is not available in the medical records/EHR during the baseline visit if feasible.

6.1.1.4 Treatment information

Information on treatment with pembrolizumab per the treating physician's discretion in routine clinical practice will be collected and recorded by the study investigators/staff during the study period. The start and stop dates for the administration of pembrolizumab and number of cycles given to the patient will be recorded. If dose modification is made during the course of treatment, the date will be recorded, along with the reason(s) for the modification. In addition, during the study period, use of cancer-related concomitant medications will also be recorded by the investigator of study staff.

Spontaneous, patient and/or investigator-reported TEAEs within the study follow up period will be recorded by the study investigator/staff per the specifications in section 7. The study investigators will determine the severity of the TEAEs based on the NSCI CTCAE v5 severity grading.

6.1.4 Clinical outcomes

The timing of clinical outcome assessments will take place per routine clinical schedules. The typical clinical practice in Taiwan for the assessment of tumor responses takes place approximately 2-3 months after the initiation of the treatment. Prior to the beginning of this study, an investigators' meeting will take place to review study design, procedures, and standards. It will be emphasized to all investigators that, it is important to keep the assessment visit schedule as close to 2-3 months as much. In addition, it will be re-

Protocol/Amendment No.: 1.1 (14 Sep 2019)

VEAP ID NO: 8439

Epidemiology No.: EP05026.058

iterated that RECIST version 1.1 should be used for the assessment. Tumor response will be categorized as CR, PR, PD, and SD per RECIST. The basis (clinical, pathologic, radiologic, combination, etc.) for the response assessment, and the date the assessment is performed will also be recorded.

Survival information will be collected periodically from medical records, contact through site investigators or from Taiwan death registry for up to two years from end of follow up for all participants. This information will be used for PFS and DoR assessments among responders.

6.1.4.1 Withdrawal/Discontinuation

When a subject discontinues/withdraws prior to trial completion, all applicable activities scheduled for the final trial visit should be performed at the time of discontinuation.

7 Safety Reporting and Related Procedures

Introduction

This is a primary data collection non-interventional study being conducted within routine medical practice. All direction for medication usage is at the discretion of a physician in accordance with usual medical practice. No administration of any therapeutic or prophylactic agent is required in this protocol, and there are no procedures required as part of this protocol.

7.1 Adverse Event Reporting

7.1.1 INVESTIGATOR RESPONSIBILITY:

If the investigator becomes aware of any serious adverse event (SAE), including death due to any cause, or non-serious adverse reaction (NSAR) following the use of pembrolizumab, or any other Merck product, the event must be reported according to Table 2. The investigator must evaluate each SAE for causality and record causality on the AE form for each event reported.

Similarly, pre-specified Health Outcomes of Interest (HOIs) that meet criteria for SAE/NSAR, special situations, and any spontaneously reported AEs must be reported according to Table 2.

Protocol/Amendment No.: 1.1 (14 Sep 2019)

VEAP ID NO: 8439

Epidemiology No.: EP05026.058

Table 2: AE Reporting Timeframes and Process for Investigators and Vendors

EVENT TYPE	INVESTIGATOR TIMEFRAME	VENDOR TIMEFRAME
	Investigator to	Vendor to Merck
	Vendor [1], [2]	[3]
SAE, regardless of causality (primary data collection)	24 hours from receipt	2 BD/3 CD from time
Serious pre-specified HOI		of receipt from
Serious Special Situation, regardless of causality		investigator
NSAR	10 CD from receipt	10 CD from time of
Non-Serious pre-specified HOI if NSAR	_	receipt from
Non-serious Special Situation, regardless of causality		investigator

Spontaneously reported adverse events for Merck products-submit using above timeframes

If the investigator elects to submit AEs for **non-Merck products**, they should be reported to the market authorization holder (MAH) for that product or to the health authority according to the institution's policy or local laws and regulations. Note: Per [2], below, AEs for comparators must be entered in study database.

Follow-up to any event-submit using above timeframes

BD-Business Day; CD-Calendar Day

- [1] AE reports from investigators must be transmitted via fax, secure email (if available), or entered directly into vendor's electronic data collection (EDC) platform, if utilized.
- [2] Investigator to Vendor: Applies to events for Merck study product, non-Merck comparators, and other Merck products when a VENDOR is managing AE reporting from investigator to Merck. Events for Merck study product and non-Merck comparators are entered in study database for tabulation in study report. Events for other Merck products are not entered in study database but must be forwarded to Merck for regulatory reporting.
- [3] Vendor to Merck: Applies to events for Merck study product and other Merck products if the vendor is managing AE reporting between investigator and Merck. Not applicable for studies not using a vendor for AE reporting.

Submitting AE reports to Merck: All AEs must be submitted to Local PV Taiwan: FAX:
, in English using an AE form (attached) for reporting to worldwide regulatory agencies as appropriate.

7.1.2 STUDY REPORT:

Protocol/Amendment No.: 1.1 (14 Sep 2019)

VEAP ID NO: 8439

Epidemiology No.: EP05026.058

The final study report, and any planned interim analysis, will include aggregate listings of all events collected for pembrolizumab and will be provided to regulatory agencies by the sponsor as required.

7.1.3 PERIODIC SAFETY UPDATE REPORTS:

Any relevant safety information will be summarized in the appropriate Periodic Safety Update Report (PSUR)/Periodic Benefit Risk Evaluation Report (PBRER) and/or Development Safety Update Reports (DSUR) if required.

7.2 **DEFINITIONS**

7.2.1 Adverse Event (AE)

Any untoward medical occurrence in a patient or clinical investigation subject administered sponsor's product and which does not necessarily have to have a causal relationship with this product. An adverse event can therefore be any unfavorable and unintended sign (including an abnormal laboratory finding, for example), symptom, or disease temporally associated with the use of the product, whether or not considered related to the product. Any worsening (i.e., any clinically significant adverse change in frequency and/or intensity) of a preexisting condition that is temporally associated with the use of the product, is also an adverse event.

7.2.2 Adverse Reaction (AR); also referred to as Adverse Drug Reaction (ADR)

An AE which has a causal relationship with the product, that is, a causal relationship between the product and the adverse event is at least a reasonable possibility.

7.2.3 Serious Adverse Event (SAE)/Serious Adverse Reaction (SAR)

An adverse event or adverse reaction that results in death, is life threatening, results in persistent or significant disability/incapacity, requires inpatient hospitalization, prolongation of existing inpatient hospitalization, is a congenital anomaly/birth defect, or is another important medical event. Other important medical events that may not result in death, may not be life-threatening, or may not require hospitalization may be considered an SAE/SAR when, based upon appropriate medical judgment, they may jeopardize the patient or subject and may require medical or surgical intervention to prevent one of the other outcomes listed previously. Examples of such medical events include allergic bronchospasm requiring intensive treatment in an emergency room or at home and blood dyscrasias or convulsions that do not result in inpatient hospitalization.

7.2.4 Non-serious Adverse Reaction (NSAR)

Protocol/Amendment No.: 1.1 (14 Sep 2019)

VEAP ID NO: 8439

Epidemiology No.: EP05026.058

An adverse reaction that does not meet any of the serious criteria in 7.2.3.

7.2.5 Special Situations

The following special situations are considered important safety information and must be reported, regardless of seriousness or causality, if the investigator becomes aware of them:

- Overdose
- Exposure to product during pregnancy or lactation
- Lack of therapeutic effect
- Off-label use, medication error, misuse, abuse, or occupational exposure
- Suspected transmission via a medicinal product of an infectious agent
- Unexpected Therapeutic Benefit/Effect

7.2.6 Health Outcome of Interest (HOI)

Health Outcomes of Interest (HOIs) are pre-specified clinical events or outcomes that are collected according to the protocol. HOIs may be represented as diagnosis, treatment or procedures. Examples of HOIs include syncope or hypoglycaemia collected as study endpoints. HOIs must be assessed as part of AE collection and may meet criteria for AE reporting. Specifically, the investigator must assess each HOI for serious criteria and causality. If the HOI meets criteria specified in the protocol for AE reporting, then it must be reported as such.

7.2.7 Sponsor's product

Sponsor's product includes any pharmaceutical product, biological product, device, diagnostic agent or protocol-specified procedure, whether investigational (including placebo or active comparator product) or marketed, manufactured by, licensed by, provided by or distributed by the Sponsor for human use.

7.2.8 Causality Assessment

A causality assessment is the determination of whether or not there is at least a reasonable possibility that a product caused the adverse event. Causality must be recorded on the AE form by the investigator for each reported event in relationship to a Sponsor's product.

Primary Data Collection

Protocol/Amendment No.: 1.1 (14 Sep 2019)

VEAP ID NO: 8439

Epidemiology No.: EP05026.058

The assessment of causality is to be determined by an investigator who is a qualified healthcare professional according to his/her best clinical judgment. Use the following criteria as guidance (not all criteria must be present to be indicative of causality to a Sponsor's product): There is evidence of exposure to the Sponsor's product; the temporal sequence of the AE onset relative to the administration of the Sponsor's product is reasonable; the AE is more likely explained by the Sponsor's product than by another cause.

7.3 Adverse Event Reconciliation

AE reconciliation will be performed between the safety database and study data to ensure all reportable events were reported and received. Starting from when the first patient is enrolled through the end of data collection, all reportable events will be reconciled on a periodic basis.

8 Product Quality Complaint Reporting

8.1 INVESTIGATOR RESPONSIBILITY:

Any occurrence of a product quality complaint for a Merck product identified during the conduct of the study, must be reported by the study investigator or qualified designee using the Product Quality Complaint (PQC) Reporting Form following the directions in Table 3. The PQC Reporting Form must be fully completed in English. Once the PQC Reporting Form is submitted, the investigator or designee may be contacted for further information.

If both an AE and a PQC occur, the AE should be reported according to the AE reporting requirements in the protocol and the PQC should be reported per Table 3.

Table 3: PQC Reporting Timeframes and Process for Investigators

EVENT TYPE	INVESTIGATOR TIMEFRAME	
	Investigator to Merck	
PQC	24 hours from receipt	
PQC reports must be submitted via e-mail by the investigator to the local designated point of contact (DPOC) using a PQC form.		
Submitting PQC reports to Merck: All PQCs must be submitted to the local DPOC in English using a PQC form (attached). The following e-mail addresses should be used by country:		

8.2 DEFINITIONS

Protocol/Amendment No.: 1.1 (14 Sep 2019)

VEAP ID NO: 8439

Epidemiology No.: EP05026.058

8.2.1 Product Quality Complaint (PQC).

Any communication that describes a potential defect related to the identity, strength, quality, purity or performance of a product identified by an external customer. This includes potential device or device component malfunctions.

8.2.2 Malfunction

The failure of a device (including the device component of a combination product) to meet its performance specifications or otherwise perform as intended. Performance specifications include all claims made in the labeling for the device.

9 Statistical Analysis Plan

9.1 Statistical Methods

The analyses will be of descriptive nature in this study. The study is not aimed to test any pre-specified hypothesis. All analyses will be performed by the sponsor or designee after the completion of the study and the study data files are locked and released.

9.1.1 Primary Objective(s): Calculation of Epidemiological Measure(s) of Interest (e.g. descriptive statistics, hazard ratios, incidence rates, test/retest reliability)

Descriptive analysis, including univariate analyses and cross tabulations, will be used for presenting baseline demographic and clinicopathological characteristics of the MSI-H/dMMR patients included in this study. Frequencies or mean and/or median will presented for discrete and continuous variables, respectively, with corresponding 95% confidence intervals (CIs). In addition, frequency of MSI/MMR testing method will also be presented to provide additional context.

ORR is defined as the combined proportion of patients with a CR or PR tumor response per the investigator's assessment, presented as a percentage with corresponding 95% CI. The primary analysis will be on combined ORR with all patients included in the study.

DoR is measured from the time of initial response until the time at which it is determined that tumor progression occurs. Kaplan-Meier plots will be generated to describe DoR with median DoR estimated along with the corresponding 95% CI.

Subgroup analyses in individual caner types for ORR and DoR will be performed only if adequate number (>5) of patients have the specific cancer.

9.1.2 Secondary Objective(s): Calculation of Epidemiological Measure(s) of Interest (e.g. hazard ratios, incidence rates, test/retest reliability)

TEAEs will be summarized for the study population using the NCI CTAE version 5. Frequencies with corresponding 95% CIs will be calculated by MedDRA system organ class (SOC), and worst

Protocol/Amendment No.: 1.1 (14 Sep 2019)

VEAP ID NO: 8439

Epidemiology No.: EP05026.058

CTCAE grade. These analyses will be performed for TEAEs, drug-related TEAEs, treatment-emergent SAEs, drug-related treatment-emergent SAEs, and TEAEs leading to dose modification, interruption, or permanent dose discontinuation.

PFS is defined as the length of time between the day on which the first dose of pembrolizumab is given to the day on which PD is determined by the study investigator, or the day of death, whichever happens first. Kaplan-Meier plot will be generated to describe the PFS in the study population. Univariate analysis of PFS will be performed and the median PFS along with inter-quartile range will be reported with 95% CIs.

OS in this study is the length of time measured from the day on which the first dose of pembrolizumab is given to the day of death (of any cause). Similar analyses as performed for PFS will be performed for OS.

For PFS and OS, for patients with no events, the censoring date will be the last date of tumor response assessment performed and the last date the patient is seen alive during the study period. Subgroup analyses in individual caner types may be performed for PFS and OS, if there are at least >5 cancer patients in the subgroup.

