Study Duration	The recruitment period is estimated to take at least 2 years, depending on the speed of uptake of pembrolizumab; and all patients who respond to the treatment of pembrolizumab will be followed through the registry for a minimum of 1 year following response to measure duration of response.		
Exposure and Outcome	The exposure of interest in the proposed study is treatment with pembrolizumab. The primary outcome is patient's response to pembrolizumab treatment (complete response, partial response, stable disease, or progression). Response to treatment will be assessed using Response Evaluation Criteria in Solid Tumors (RECIST) 1.1. Duration of response will also be described among those who respond to the treatment of pembrolizumab.		
Statistical Methods	Descriptive analyses will be performed to report the patients' characteristics, and objective response rate among patients received pembrolizumab. Specifically, frequencies with corresponding 95% confidence intervals will be used to describe the patients' characteristics. For clinical outcomes, proportion of the objective response rate and corresponding 95% confidence interval will be reported. Kaplan-Meier survival curves will be used to report the duration of response. If median		

Product: MK-3475
Protocol/Amendment No.: 1.1 (14 Sep 2019)
VEAP ID NO: 8439

Epidemiology No.: EP05026.058

	duration of response is reached within the study follow-up period, then it will also be reported.
Sample Size and Power Calculations	The study sample size was mandated by the Taiwanese regulatory agency. The proposed study will include 20 patients meeting the study inclusion/exclusion criteria. The 20-patient sample size produces a two-sided 95% confidence interval with a precision (half-width) equal to 19% for the response rate, assuming a 20% objective response rate.

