4.2 Outcomes

This study will capture both clinical and safety outcomes for each participating patient. All investigators will be requested to use Response Evaluation Criteria in Solid Tumors (RECIST) 1.1 and/or a disease-specific tumor response measurement that are commonly used and accepted for determining tumor responses. The primary clinical outcome is tumor response, which will be categorized into complete response (CR), partial response (PR), progressive disease (PD), and stable disease (SD). The tumor responses will be determined by the investigators who treat the cancer patient, subsequent to an investigators' meeting to reiterate the essential elements to standardize the diagnostic criteria. Date of assessment and the basis of assessment will be captured. The assessment of tumor response will be performed as in routine clinical setting without a study-specified visit schedule. Death is also a clinical outcome and will be captured during the study period. With the collected tumor response and death information, objective response rate (ORR) can be derived. Duration of response (DoR) will also be captured among the responders. Specific definitions of these endpoints are provided in the Statistical Analysis Plan section (section 9). Survival information for both responders and non-responders will be collected periodically from medical records, contact through site investigators or from Taiwan death registry for up to two years from end of follow up.

Safety information regarding TEAEs will be recorded as reported by the patients and/or the treating physicians in course of routine clinical care, without further prompting. TEAEs are AEs that occur sequent to the first administration of the first dose of pembrolizumab. Definitions for AE and SAE are provided in section 7. The severity of

Protocol/Amendment No.: 1.1 (14 Sep 2019)

VEAP ID NO: 8439

Epidemiology No.: EP05026.058

the TEAEs will be assessed and determined according to the National Cancer Institute (NCI) Common Terminology Criteria for Adverse Events (CTCAE) version 5 severity grading.

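### The primary ORR counts a CR or PR with no requirement that it persist; a confirmed ORR from assessments already recorded should be reported beside it

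*Protocol*

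**What the plan says.** Section 9.1.1 defines the primary clinical measure: "ORR is defined as the combined proportion of patients with a CR or PR tumor response per the investigator's assessment". The primary analysis pools all included patients. The next definition reads "DoR is measured from the time of initial response until the time at which it is determined that tumor progression occurs". Neither sentence asks for a second assessment, a minimum interval or a rule for combining serial readings.

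Section 4.2 refers the reader to section 9 for the specific endpoint definitions, so these are the operative ones. On the assessor it says: "The tumor responses will be determined by the investigators who treat the cancer patient". It names RECIST 1.1 but adds "and/or a disease-specific tumor response measurement that are commonly used and accepted for determining tumor responses". Section 6.1.4 names RECIST 1.1 and provides that "The basis (clinical, pathologic, radiologic, combination, etc.) for the response assessment, and the date the assessment is performed will also be recorded".

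On follow-up, the Protocol Summary (Study Duration) states that responders "will be followed through the registry for a minimum of 1 year following response to measure duration of response"; section 3.1 ends this at death if earlier. Sections 4.2 and 6.1.4 leave the timing of tumor assessments to routine care.

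**The concern.** On its plain reading, section 9.1.1 lets one CR or PR call make a responder, whatever the next assessment shows. There is no comparator in which the same error would also appear, the assessor knows the treatment, and a call need not be radiologic. Measured against the rate of responses that persist, counting transient calls can only raise ORR.

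ORR and DoR are the study's primary clinical outcomes. Section 1.1.2.4 says the indication rests on response rate and durability, and section 1.2 says the registry is to complement the submission data. A reader will therefore want to know how many of the counted responses lasted to a second look. As written, the report need not say, although dates and bases of assessment are to be recorded.

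**Working it through.** **Inputs from the protocol.** N = 20; planning ORR 20%; half-width 19% (section 9.3, Table 4); non-CRC trial ORR 37.2% (section 9.3); non-CRC median PFS 5.4 months (section 3.1); typical assessment 2-3 months after treatment start (section 6.1.4). **Not in the protocol:** the rate of transient CR or PR calls, which is assumed below.

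**1. The plan's own figure.** The exact (Clopper-Pearson) 95% interval for 4/20 is 5.7% to 43.7%; (43.7 - 5.7)/2 = 19.0, matching the stated 19%. The other rows match too: exact half-widths of 15.2, 21.2, 22.4 and 22.8 against the stated 15, 21, 22 and 23. Wald (17.5) and Wilson (16.8) do not give 19.

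**2. Effect of one transient call.** 1/20 = 5.0 points; 5.0/19 = 0.26 of the half-width.

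**3. What a reader would see**, if 6 of 20 patients are recorded as responders:

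| Not confirmed | Confirmed ORR | Exact 95% CI |
|---|---|---|
| 0 | 6/20 = 30.0% | 11.9-54.3% |
| 1 | 5/20 = 25.0% | 8.7-49.1% |
| 2 | 4/20 = 20.0% | 5.7-43.7% |

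**4. Assumed share of non-responders with a transient call.** At a 20% ORR there are 20 x 0.80 = 16 non-responders.
- 3%: 16 x 0.03 = 0.48 extra responders; 0.48/20 = 2.4 points; 0.48/4.48 = 11% of the DoR set.
- 10%: 16 x 0.10 = 1.6 extra responders; 1.6/20 = 8.0 points; 1.6/5.6 = 29% of the DoR set.

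**5. The same question per assessment.** With chance f of a transient call at each of K assessments, observed ORR = p + (1 - p)(1 - (1 - f)^K). At p = 20%:

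| f | K = 1 | K = 2 | K = 4 |
|---|---|---|---|
| 1% | +0.8 | +1.6 | +3.2 |
| 2% | +1.6 | +3.2 | +6.2 |
| 5% | +4.0 | +7.8 | +14.8 |

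At p = 37.2% the range is +0.6 to +11.6 points. If assessments recur every 2-3 months, a median PFS of 5.4 months allows 5.4/3 = 1.8 to 5.4/2 = 2.7 looks. K near 2 is then the realistic column and K = 4 is an upper bound.

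**6. Effect on DoR.** DoR ends at progression. A transient PR followed by PD at the next assessment adds a short duration. A transient PR followed by a return to stable disease does not end DoR, so that patient contributes the whole later stable period. The first pulls the curve down and the second can pull it up. The protocol gives no basis for saying which would dominate.

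**The case against.** The strongest reply is that section 9.1.1 is silent rather than wrong. RECIST 1.1 is named, an investigators' meeting is to standardise the criteria, and deriving one best response from serial readings is commonly left to a separate analysis plan. The study is also descriptive: sections 9.2.1 and 9.2.2 warn against direct comparison with the trials, and section 9.2.2 concedes variation between assessors. The assumed 2.4-8 points lies well inside the 19-point half-width. Errors also run the other way, since a true PR may be read as stable disease, and patients never assessed stay in the denominator.

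Part of this stands. No hypothesis is tested, so the consequence is a shifted estimate and not a false-positive finding. Missed responses could offset transient ones relative to the truth. What remains is that section 4.2 makes section 9 the place of definition, that confirmation is mentioned nowhere, and that criteria other than RECIST are allowed. The stated limitations do not tell a reader that a response seen once and then lost still counts.

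A reader might infer three stronger things that the protocol does not support:
- *That a later scan will exist for every responder.* Follow-up is planned for all responders, but scans follow routine care and follow-up stops at death.
- *That ORR is biased up and DoR down.* Because stable disease does not end DoR, its direction is open.
- *That the DoR curve should be restricted to confirmed responders.* Dated from first response, such a curve contains guaranteed progression-free time up to the confirming assessment and drops genuine short responders.

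**Conclusion.** The point holds as a modest, inexpensive improvement. Section 9.1.1 sets no persistence requirement, so the any-response ORR is at or above the persistent-response rate, by exactly 5 points for each transient call at N = 20. How many such calls will occur is unknown. The 2.4-8 points rests wholly on the assumed 3-10% of 16 non-responders, and the wider per-assessment assumptions give about 1 to 15 points. With about four responders expected at the planning ORR, even one transient call would be a visible share of the DoR set, but its effect on the DoR curve could go either way.

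**What to change.** In section 9.1.1:

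1. Keep the any-response ORR, with its 95% CI, as the primary figure.
2. Add a confirmed ORR with its 95% CI over all included patients: CR or PR still present at the next recorded tumor assessment at least 4 weeks later, with no PD in between.
3. Report responders with no later assessment as not evaluable for confirmation, separately from those whose response was contradicted.
4. Keep DoR on all responders as now. Show DoR in confirmed responders only as a supportive display, with a note that it includes guaranteed progression-free time up to the confirming assessment.

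The cost is a few sentences and one added analysis of dates and assessments already to be recorded, with no extra scan or visit. The downside is that confirmed ORR will be somewhat lower, partly because routine care may not supply a second assessment for everyone; item 3 makes that part visible.

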2.1 Primary Objective(s) & Hypothesis(es)

In an observational study in advanced MSI-H cancer patients treated with pembrolizumab and followed prospectively,

- 1) describe demographic and clinicopathological characteristics; and
- 2) describe clinical objective response rate and duration of response

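### Duration of response, part of primary objective 2, ends only at progression, so a responder's death without documented progression is not an event, contrary to PFS and to section 6.1.4

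*Protocol*

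**What the plan says.** Primary objective 2 (protocol section 2.1) is to "describe clinical objective response rate and duration of response". Section 4.2 refers the reader to section 9 for the endpoint definitions, so section 9 governs.

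Section 9.1.1 defines the outcome: "DoR is measured from the time of initial response until the time at which it is determined that tumor progression occurs". The analysis follows: "Kaplan-Meier plots will be generated to describe DoR with median DoR estimated along with the corresponding 95% CI".

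Two other places bear on death:

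- Section 9.1.2 runs PFS from the first dose "to the day on which PD is determined by the study investigator, or the day of death, whichever happens first".
- Section 6.1.4 collects survival information from medical records, site contact and the national death registry for up to two years after the end of follow-up, and adds: "This information will be used for PFS and DoR assessments among responders".

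The censoring rule in section 9.1.2 names PFS and OS only. DoR has none.

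**The concern.** Three parts of the protocol treat the death of a responder differently. Section 9.1.1 gives it no role in DoR, section 9.1.2 makes it an event for PFS, and section 6.1.4 says survival data will be used for DoR without saying how. An analyst who follows section 9.1.1 literally would not count a death without documented PD as the end of response. The usual way to carry that into a Kaplan-Meier analysis is to censor the patient, which assumes that the response would have continued like that of the remaining responders.

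The protocol makes such deaths plausible. Tumor assessments follow routine care with no study schedule (sections 4.2 and 9.2.2), so a patient can die before a scan shows progression. Section 3.1 ends a responder's follow-up at death, so deaths within the DoR window are foreseen. Durability also matters to the purpose of the registry: section 1.1.2.4 states that the indication was approved on response rate and durability of response.

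This is not a detail left for a later analysis plan. The protocol states the definition itself, in its own section headed Statistical Analysis Plan.

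**Working it through.** **The plan's own figure.** The only design figure is for ORR; none is given for DoR. The 19% half-width at N = 20 and ORR 20% is reproduced by the exact (Clopper-Pearson) interval for 4/20, which is 5.7% to 43.7%: (43.7 - 5.7)/2 = 19.0. Nothing below alters it.

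**Step 1: what happens to a responder who dies without documented PD.**

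| Source | Role of the death |
|---|---|
| 9.1.1, DoR definition | Not an end of response |
| 9.1.2, PFS definition | Event |
| 9.1.2, censoring rule | Covers PFS and OS only |
| 6.1.4 | Survival data are to be used for DoR; no rule |

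The definition makes the death a non-event. The censoring date is not stated.

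**Step 2: direction if the death is censored at the date of death.** Counting the death as an event multiplies the Kaplan-Meier curve by (1 - 1/n), with n the number at risk; censoring omits that factor. The patient leaves the risk set at the same time either way, so all later factors are identical. The curve with deaths censored is therefore never below the curve with deaths counted.

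**Step 3: size under constant hazards.** Let h be the hazard of PD or death, and q the share of first events that are deaths without PD. With those deaths censored, the estimated hazard is (1 - q)h and the median is ln 2/[(1 - q)h] = M/(1 - q), where M is the true median of time to PD or death. The value M = 12 months is an illustration only.

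| q (assumed) | 1/(1 - q) | Apparent median if M = 12 months | Apparent 12-month proportion, 0.5^(1 - q), against a true 50% |
|---|---|---|---|
| 0 | 1.00 | 12.0 | 50.0% |
| 10% | 1.11 | 13.3 | 53.6% |
| 20% | 1.25 | 15.0 | 57.4% |
| 30% | 1.43 | 17.1 | 61.6% |

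**Step 4: small numbers.** Expected responders are 20 × 0.20 = 4 at the assumed ORR, or 20 × 0.372 = 7.4 at the non-CRC rate quoted in section 9.3. Take four invented responders: PD at 3 months, death without PD at 5, PD at 8, and one censored at 12. The median is the first time the curve is at or below 50%.

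- Death counted: 3/4 = 0.75 at 3 months, then 0.75 × 2/3 = 0.50 at 5. The median is 5 months.
- Death censored at 5: 0.75 at 3 months, then 0.75 × 1/2 = 0.375 at 8. The median is 8 months.

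**Step 5: a different censoring date.** Take four invented responders with PD at 5, 8 and 10 months; the fourth was last scanned at 3 and died at 20.

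- Censored at the last scan (month 3): S(8) = 2/3 × 1/2 = 33%.
- Death counted at 20: S(8) = 3/4 × 2/3 = 50%.
- Censored at death (month 20): S(8) is also 50%, but the curve stays at 25% after month 10 instead of falling to 0 at month 20.

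The direction in step 2 therefore holds against censoring at the date of death. It need not hold against censoring at the last scan.

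**The case against.** The strongest reply is that the overstatement is inferred. Section 9.1.1 gives no censoring rule for DoR, and section 6.1.4 suggests that deaths were meant to enter it. On that view the documents show an unreconciled inconsistency, not a settled decision to censor deaths. This stands as a limit on the claim: the upward effect is conditional on how deaths are handled. It does not rescue the definition, because section 9 governs and names progression alone.

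Nothing in the documents informs q, and there is no effect if every responder who dies has documented PD first. That also stands. A reader might infer from the unscheduled assessments that death commonly precedes documented progression, but no rate is given.

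A reader might also conclude that section 6.1.4 cannot be carried out under section 9.1.1. That goes too far, since survival data could still inform follow-up status or censoring dates. Nor can one put a fixed ceiling on what a single death does to the curve. With four responders it is 25 percentage points only if nobody was censored earlier; if two were, one death takes the curve from 100% to 50%.

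DoR should not be called the primary endpoint. Section 4.2 says "The primary clinical outcome is tumor response", and section 9.1.1 places the primary analysis on ORR. DoR is part of a primary objective. The study is descriptive, tests no hypothesis, and already warns that time-related outcomes will be affected by variable assessment times (section 9.2.2). This limits the consequence but does not correct the definition.

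**Conclusion.** The point holds. As written, a responder's death without documented PD is not a DoR event. This conflicts with the PFS definition in the same section and sits badly with the stated use of survival data in section 6.1.4.

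If those deaths are censored at the date of death, DoR can only be unchanged or overstated. Under constant hazards the median rises by 11%, 25% or 43% at q = 10%, 20% or 30%. The range of q is an assumption, and the effect is zero at q = 0.

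A reader might go on to infer that the section 9.1.1 rule for cancer-type subgroups, which counts patients with the cancer, must count responders for DoR. The documents do not require that. The rule is a minimum for descriptive output, and with about 4 responders expected in the whole study at 20% ORR, a threshold of more than 5 responders would in practice remove DoR subgroups altogether.

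**What to change.** In section 9.1.1, define DoR as the time from first documented CR or PR to first documented PD or death from any cause, whichever is first, with responders without an event censored at their last tumor assessment.

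Extend the censoring paragraph in section 9.1.2 to DoR, and make section 6.1.4 say how survival data enter it. State how a death long after the last tumor assessment is handled. Survival is followed for up to two years after the end of follow-up, and step 5 of the working shows that counting such a death at its date can raise the curve relative to censoring at the last scan.

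The cost is a few sentences. The death data are already to be collected. Reported DoR may become less favourable, though that is not assured in every data set. ORR and Table 4 are unaffected.
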